6.0 Study Procedures

At baseline, 3 months, 6 months, and 12 months, mothers and adolescents will complete surveys consisting of measures are widely validated and have been used successfully by our research team in previous studies. Follow-up data will be collected at regularly-scheduled diabetes clinic visits, so that questionnaire data corresponds with clinical data. The measures take about 40 minutes to complete. Mothers will also complete a measure of depression (PHQ-9) via a link emailed to them by the study team biweekly during the active phase of the intervention (first 3 months). All measures will be collected using REDCap.

Demographics - completed by mother

Responses to Stress Questionnaire (RSQ) measures 3 coping factors: primary control coping, secondary control coping, and disengagement coping - completed by mother

Multidimensional Scale of Perceived Social Support (MSPSS) - completed by mother

Patient Health Questionnaire - 9 items (PHQ-9)-completed by mother

Generalized Anxiety Disorder Scale - 7 items (GAD-7) completed by mother

Diabetes Family Conflict Scale (DFCS) - completed by mother and adolescent

Self-Care Inventory (SCI) - completed by mother and adolescent

Pediatric Quality of Life Inventory (Peds-QL) diabetes-specific module - completed by adolescent

Child Behavior Checklist (CBCL) - completed by mother

Youth Self Report (YSR) - completed by adolescent

Problem Area in Diabetes - Teen (PAID-T) - completed by adolescent

Parent Diabetes Distress Scale (PDDS) - completed by mother

Collaborative Parent Involvement Scale - completed by adolescent

Revised Brief Diabetes Knowledge Test - completed by mother

COVID-19 Questions – completed by mother and adolescent

Satisfaction Survey – completed by mother at 3 month follow-up

At baseline and 6 months data collection, adolescent-mother dyads will participate in a 15-minute videotaped conversation about diabetes-related stress. To choose the topic for the video interaction, we will use the mother's highest-rated stressor on the Response to Stress Questionnaire (Connor-Smith, Compas, Wadsworth, Thomsen, & Saltzman, 2000), completed as part of the survey data collection, which lists diabetes-specific stressors. Mothers will rate the frequency of each stressor (e.g., worrying about "bad" numbers, remembering diabetes supplies) on a 4-point Likert scale ranging from 0 (never) to 3 (almost every day). Each dyad will be given a cue card with questions regarding the highest-rated stressor (e.g., What happened the last time we [had to] you remember diabetes supplies], what kind of emotions do we have when we [have to remember diabetes supplies]? How can we reduce this stress?) to guide their discussion during the videotaped interaction. This protocol has been used successfully in other studies conducted by [name], and she has trained several cohorts of raters on the Iowa Family Interaction Rating Scales to be reliable coders.

The interaction will be recorded using study iPads. Video files will be transferred from the passcoded iPad to an encrypted study computer, and then uploaded to Enterprise Storage, the secure, shared drive. Video files will only be viewed by KSP.

Mothers in the study will have 7 individual phone calls with a trained member of our research staff to discuss the information in the binders. Calls will last approximately 10-30 minutes. Mothers assigned to the Communication & Coping group will discuss content related to coping with diabetes-related stress and positive parenting strategies, following the study manual mailed to participants after randomization. The content of this manual was reviewed by a coder trained in health literacy at Vanderbilt's Effective Health Communication Core. Each session was given a Suitability Assessment of Materials (SAM) score to objectively assess the materials for clear communication and health information design (content, literacy demand, graphics, layout and typography, learning stimulation, and cultural appropriateness). Scores of 70% to 100% are considered superior material suitable for low health literacy individuals (Doak, Doak, & Root, 1996). On the SAM scale, our sessions were rated 78% to 86%, with a reading

level of 6th-7th grade. In addition, the Patient Education Materials Assessment Tool (PEMAT) was used to assess the understandability and actionability of our intervention materials, with specific suggestions to raise these scores further (e.g., add pictures, highlight goals for each session; Shoemaker, Wolf, & Brach, 2013). On the PEMAT, the scores for individual sessions ranged from 79% to 92% (higher scores indicate that material is more understandable or actionable). All recommendations for changes were incorporated into the final versions of the manual.

Mothers assigned to the Diabetes Education group will discuss content related to diabetes management, in line with the educational materials mailed to participants after randomization. These materials were based on information available on the American Diabetes Association website (www.diabetes.org). Mothers in the Diabetes Education group will be given the option to receive the manual containing the Communication and Coping content at the 12 month visit, after the mother has completed the study. The first 5 calls will occur weekly, and the last 2 "booster" calls will occur monthly. The calls will be scheduled at a time that is convenient for study participants. These calls will be audio recorded and 20% will be randomly assessed for fidelity by an objective rater. Audio files of the intervention sessions will be stored on the same secure, shared drive and will only be accessed by trained research staff to assess fidelity or for training purposes.

Study participants will be required to "friend" the study Facebook account before they are added to the secret groups to ensure that the correct person is added. All mothers in the study will receive 1 post per day for 3 months. The posts will be on topics related to the group assignment (communication and coping or diabetes education). A moderator will view and respond to all comments made by Facebook group members. Facebook data will be extracted using programming stored on a protected server and stored in a de-identified SPSS file.

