10.0 Statistical Considerations

Baseline variables known to be associated with parenting including age, sex, income, and marital status will be compared by treatment group using the Kruskal-Wallis test (continuous variables) or Pearson's Chi-squared test (categorical variables). We will also examine if diabetes-related variables (e.g., duration of diabetes, baseline A1C) are associated with treatment group. *A priori*, we assume that our block randomization will lead to well-balanced groups so that we will not need to control for additional confounders.

Effects of the Intervention: We will estimate the effect of the intervention on each of the continuous outcomes by fitting linear mixed-effects models developed. In modeling, outcomes will be considered at their key time-points (baseline, 3 months, 6 months, and 12 months) with treatment group and the interaction of treatment with time serving as the main explanatory variables. Such a model will allow us to test for any differences between treatment and control groups over time while accounting for baseline values. While the randomized block design should minimize confounding, we will adjust for age, income, and marital status to improve precision. The results from the adjusted and unadjusted models will be compared with respect to their estimates of the treatment effects. Our interpretation will focus on describing clinically relevant treatment effects (e.g., A1C reductions of $\geq 0.5\%$, >1 additional glucose check per day, reduction from moderate to mild depressive symptoms) with corresponding confidence intervals, rather than just significance testing. We will include a random intercept to account for within-subject correlation. The error structure of the model is assumed to be compound symmetric, and the validity of this assumption will be examined by computing Akaike Information Criteria against other common structures. Subjects will be included in the analysis if they have an outcome measured at baseline and at least one outcome measured 6 or 12 months later.

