Exploratory Aim: Examine the differential impact of intervention effects across demographic factors (i.e., marital status, income, adolescent age, and sex).

While evaluating the main effects of interventions is critical to improving health outcomes, it is equally important to examine moderators of randomized clinical trials – even those that are unsuccessful – in order to determine *for whom* interventions may work. Based on findings from the literature and our own earlier work, we will examine potential moderators, with a focus on marital status, income, and adolescent age and sex. Moderators will be tested by including an interaction term with treatment group in the regression models.

Power and sample size:

We plan to enroll 154 subjects so that, after allowing for a 15% attrition rate, 130 subjects will be available for analysis. Preliminary data from our pilot study with 30 adolescents indicates that mean A1C is 9.0% with a standard deviation of 1.16% and a correlation between repeated measurements over time of 0.60. Under these assumptions, we will have 80% power to detect a 0.5% difference in A1C if 122 subjects are measured at all 4 time points or if 138 subjects are measured only twice (out of 4 possible time points). Since we expect to obtain ≥ 3 measurements on most of subjects, enrolling 130 subjects with 2 to 4 measurements each will provide sufficient power for Aim 1. For the SCI (a measure of adherence), using preliminary data in 30 subjects we estimated baseline scores of 23.6 ± 4.2 with a correlation among repeated measures over time of 0.82. With 130 subjects measured at least twice, we will have 80% power to detect a 2.0 unit change due to treatment, which is an 8.5% difference from baseline.

Power calculations for mediation models were considered assuming 130 subjects will be available for analysis. In preliminary data, partial correlations of the mediators, PHQ9 and DFC, with A1C were 0.20 and 0.51, respectively. Correlations of the mediators with treatment were 0.52 and 0.54, respectively. Under these assumptions, we have 63% power to detect an indirect effect of treatment on A1C through PHQ9 and >99% power to detect an indirect effect of treatment on A1C through DFC. Calculations assume a 0.05 significance level.

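### Research staff deliver both arms by individual calls, but neither the outcome model nor the power calculation allows for callers; if callers are arm-specific, unevenly spread, or differ in effect by arm, the standard errors will be too small

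*Combined protocol and SAP*

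**What the plan says.** Section 6.0 describes delivery by telephone: "Mothers in the study will have 7 individual phone calls with a trained member of our research staff". The control arm has the same channel: "Mothers assigned to the Diabetes Education group will discuss content related to diabetes management". Five calls are weekly and two are monthly boosters. Quality control is by sampling: "These calls will be audio recorded and 20% will be randomly assessed for fidelity by an objective rater", with a fidelity benchmark of at least 90% in section 10.0.

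Section 10.0 specifies a linear mixed model with treatment and treatment-by-time terms. Its only random effect is at subject level: "We will include a random intercept to account for within-subject correlation". Of the residuals it says "The error structure of the model is assumed to be compound symmetric", with other structures compared by Akaike's criterion. The covariates are demographic: "we will adjust for age, income, and marital status to improve precision". Caller identity appears in none of these, and the power section contains no design effect.

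The documents do not say how many callers there are, how mothers are assigned to them, whether one person makes all seven of a mother's calls, or whether a caller works in one arm or both.

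**The concern.** When staff deliver a treatment one to one, participants who share a staff member can have more similar outcomes than participants who do not. A random intercept for the subject handles repeated measures within a dyad. It still treats different dyads as independent. Comparing residual structures by Akaike's criterion adds no caller level, and the fidelity review monitors content without entering the effect model.

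If callers differ and that difference is aligned with arm, part of the between-caller variation is read as a treatment effect and the model's standard error does not reflect it. This matters here because section 10.0 puts its weight on clinically relevant effects with confidence intervals, so intervals that are too narrow affect the main reported result.

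**Working it through.** **1. The plan's own figures.** Inputs from section 10.0 (power and sample size): A1C SD 1.16, correlation between repeated measures 0.60, difference 0.5, power 80%, alpha 0.05 (taken as two-sided). For the mean of *m* measurements the effective SD is 1.16 × √[(1 + (m − 1) × 0.60)/m].

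- m = 4: 1.16 × √(2.8/4) = 0.971. The noncentral-t calculation gives a total N of 122, as stated.
- m = 2: 1.16 × √(1.6/2) = 1.038. The same calculation gives 138, as stated.

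Both figures reproduce with repeated-measures correlation alone, so they contain no allowance for callers.

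**2. Callers working in one arm only.** The plan analyses 130 dyads, or 65 per arm. The number of callers per arm (K) and the caller ICC, defined on the subject-mean outcome, are assumptions. The formulas are:

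- design effect DE = 1 + (65/K − 1) × ICC
- type I error of the unadjusted test = 2 × [1 − Φ(1.96/√DE)]

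| K per arm | ICC 0.01 | ICC 0.02 | ICC 0.05 |
|---|---|---|---|
| 2 | DE 1.31, 8.7% | DE 1.63, 12.5% | DE 2.58, 22.2% |
| 4 | DE 1.15, 6.8% | DE 1.30, 8.6% | DE 1.76, 14.0% |
| 6 | DE 1.10, 6.1% | DE 1.20, 7.3% | DE 1.49, 10.9% |
| 8 | DE 1.07, 5.8% | DE 1.14, 6.7% | DE 1.36, 9.2% |

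For example, K = 4 and ICC = 0.02 gives 1 + 15.25 × 0.02 = 1.305, √1.305 = 1.142, 1.96/1.142 = 1.716, and a type I error of 8.6%. A 10,000-run simulation with 4 callers per arm and no caller term in the analysis gave 8.4% at ICC 0.02 and 14.2% at ICC 0.05.

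**3. Power, kept separate for two different tests.** Start from an 80% design (1.96 + 0.84 = 2.80) with 4 callers per arm.

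- Planned, unadjusted test: Φ(0.84/√DE) = 78% / 77% / 74% at ICC 0.01 / 0.02 / 0.05. This power comes with the inflated error in the table.
- Test held at a true 5% with known variance: Φ(2.80/√DE − 1.96) = 74% / 69% / 56%.

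**4. Callers serving both arms in balance.** With 4 callers, the same effect in each arm and no caller term, simulated type I error was 4.7% / 4.3% / 4.4% at ICC 0.02 / 0.05 / 0.10. The common caller effect cancels from the treatment contrast.

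**5. Callers serving both arms, with effects that differ by arm.** With 4 callers and a caller-by-arm ICC of 0.01 / 0.02 / 0.05, 20,000 runs gave 6.3% / 8.8% / 13.9%, close to the arm-specific case.

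**The case against.** A reader might infer that any difference between callers makes the standard errors too small. The documents do not support that: under balanced crossing with a common caller effect, the unadjusted analysis holds its level (step 4). Section 6.0 uses one description of the calling staff for all mothers. That does not establish crossing, but it gives no sign of arm-specific callers either.

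A reader might also infer that a few callers each serve many mothers, and that each mother has one caller throughout. Neither is stated. Several callers per mother would dilute the clustering, and a study planned for 5 years could use more callers, which shrinks the effect. No document figure supports a particular caller ICC for A1C, which is measured in the adolescent while the calls are with the mother. Manualised content and fidelity checks are meant to limit differences in delivery.

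Nor should 56% be read as the power of the planned analysis. It belongs to a test corrected to a true 5%; the planned test has about 74% at the same ICC.

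Finally, a caller effect in the primary model could be expensive. With arm-specific callers, the small-sample degrees of freedom can fall towards 2K − 2. At 4 callers per arm that is 6 (critical t 2.45), with power of about 59% / 54% / 43% at ICC 0.01 / 0.02 / 0.05. At 2 per arm it is 2 (critical t 4.30), with power of about 29% / 25% / 18%. These are worst cases.

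All of this stands, and it limits both the claim and the remedy. It does not remove the gap. The two arms deliver different content, coping and parenting coaching against diabetes education, so caller effects that differ by arm are plausible, and balanced crossing alone would then not protect the intervals. The plan specifies neither the crossing nor a way to check it.

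**Conclusion.** The point holds conditionally. The plan has no caller term, its power figures make no allowance for callers, and it leaves caller allocation unspecified. If callers are arm-specific, unevenly spread, or differ in effect by arm, the standard errors are too small. At an assumed 4 callers per arm and ICC 0.01 to 0.05, the true standard error is 1.07 to 1.33 times the model's, and type I error is about 7% to 14%. If callers serve both arms in balance with equal effects, there is no inflation. Because the documents do not say which case applies, they do not settle whether there is an error or how large it is. This is an inexpensive safeguard for the confidence intervals and does not show that the primary model is wrong.

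**What to change.** **Section 6.0.** State the planned number of callers and how mothers are assigned to them. Record the caller's ID for every call. For calls already made, recover it from the audio recordings or call records; section 11.0 has digital files erased after the study, so this must be done before then.

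**Section 10.0, effects of the intervention.** Keep the planned model as primary. Prespecify a sensitivity analysis that adds a random caller effect on follow-up outcomes, nested in arm, or caller-by-arm if callers serve both arms, with small-sample (Kenward-Roger) degrees of freedom. Report the caller ICC and the adjusted confidence interval beside each treatment effect.

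**Section 10.0, power.** State that the 80% assumes no caller clustering, and show power over a range of ICCs for the planned number of callers.

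**Cost.** One data field, some extra analysis and a less favourable power statement. If callers are few, the variance component will be imprecise and the sensitivity intervals may be much wider, which is why the adjusted model is not proposed as primary.

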7.0 Risks

Data collection requires participants (adolescents and mothers) to spend approximately 40 minutes at each collection (baseline, 3 months, 6 months and 12 months) completing surveys. At baseline and 6 months, they will spend an additional 15 minutes in a videotaped interaction.

Mothers will engage in 7 intervention phone calls that will last 30-45 minutes (the first 5 sessions will occur weekly, and the 2 booster sessions will occur monthly). In addition, we expect mothers to spend approximately 5 minutes per day reviewing Facebook posts. This is not anticipated to be an undue burden for the participants.

We will download data from the Facebook group including posts, comments, and reactions from the participants so that we can study these data to better understand how people participate in this component of the program. We will not download any data from participants' Facebook profiles or any posts to their feeds - only the posts, comments, and the posts/comments that participants react to in the study Facebook group.

The potential benefit of this study is the provision of new knowledge about innovative ways to improve diabetes management in adolescents with type 1 diabetes. In sum, the low risk of this study appears to be far outweighed by the larger, more compelling potential benefits.

Possible risks in the study include release of confidential data, worsening depression symptoms in mothers, indication of depression in adolescents, reports of harm to self or others, and reports of child abuse or neglect.

If mothers report severe symptoms of depression (PHQ-9 score of 20 or higher) or endorse the 9th item on the PHQ-9, indicating thoughts of self-harm, we will follow up with a depression protocol. A member of the research team will give the mother the resources handout, which includes crisis hotline numbers and mental health services. The PI (or the clinic social worker, if available) will follow up with the mother within 48 hours to discuss and will refer her to the ER or crisis hotline if needed.

If adolescents endorse items on the Youth Self Report (YSR) measure pertaining to suicide or self-harm, we will follow the following procedure for self-harm assessment. Item 18 asks individuals to rate from 0-2 (how often) "I deliberately try to hurt or kill myself." Similarly, item 91 reads "I think about killing myself." Scores of 1 indicate "sometime" and 2 indicate "usually." When the YSR is given during study enrollment, researchers will immediately check items 18 and 91. If a 1 or 2 is indicated on either of these items, the Pediatric Endocrinology social worker will be paged and will complete a risk assessment following clinic protocol. The PI will also be notified. If the clinic social worker is not available, research staff will administer the Columbia Suicide Severity Rating Scale (C-SSRS). If information gathered from the C-SSRS indicates low risk (non-specific ideation, no plan), individuals will be given information on local behavioral health resources and informed that the PI will check in with them within the next 48 hours. If the C-SSRS indicates high risk or risk is ambiguous the clinic social worker will be contacted again for further assessment and/or to transfer the patient for psychiatric evaluation. If the clinic social worker cannot be reached, the researcher will accompany the patient and their caregiver to the Children's Emergency Department for psychiatric evaluation.

We will download data from the Facebook group including posts, comments, and reactions from the participants so that we can study this data to better understand how people participate and how much response our posts garnered from the group. We will not download any data from participants' Facebook profiles or any posts to their feeds - only the posts, comments, and the posts/comments participants react to in the study Facebook group.

All children will receive clinical care throughout the course of the study. All diabetes treatment decisions will be made by the diabetes treatment team. All patients have access to the treatment team 24 hours/day and 7 days per week. Participants will be informed that they may discontinue the study at any time or skip any questions they do not feel comfortable answering. There are no potential legal or social risks to participants consenting to participate in this investigation. Parents will be told to follow the diabetes clinic providers' guidance on any questions related to diabetes management.

Any comments made during intervention calls or on the Facebook group that suggest the abuse of, neglect of, or inappropriate interactions with minors will be reported to the State of Tennessee Child Abuse Hotline (or the appropriate authority of the state in which the child resides). All research staff at all sites will complete annual training in Protection of Minors, and all research staff will be mandated reporters.

The PI will ensure that the trial is conducted according to the approved protocol and will be responsible for carrying out the data safety monitoring plan, which includes:

- Review of study components for data completeness and accuracy as well as protocol compliance
- Evaluate adverse events (AEs, described below) for severity, relationship to the research and actions to be taken
- Promptly report all severe AEs and unanticipated problems to the data and safety monitoring board, IRB, and NIH

KSP will complete human subjects training prior to any contact with participants and maintain annual training. KSP will also complete Good Clinical Practice training for social and behavioral research annually.

8.0 Reporting of Adverse Events or Unanticipated Problems involving Risk to Participants or Others

Any adverse events occurring during the course of this trial will be collected, documented and reported by the PI ([name]), to the Data and Safety Monitoring Board, along with reporting to the NIDDK and institutional review boards as required. Although not anticipated, if any event is identified that may have caused any type of harm to a participant, study accrual will be immediately halted until the study team and DSMB can review the event and determine if any study procedures need to be revised. Study accrual will only resume after review of study protocol has been completed and any recommended revisions made as suggested by the DSMB.

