3-9-22	Consent + Compensation	We want to offer \$20 gift cards for completion of 6-month parent-child interaction videos to incentivize collection of this data point. These gift cards will be funded by the VUMC Division of Pediatric Psychology.	We were not able to collect parent-child interaction videos at baseline or the 6-month time point during the transition to a remote protocol, and we are not able to use 6-month videos that would not have a corresponding baseline video. Because of this, we have collected less 6-month videos than expected. Also, because of the switch to a remote protocol, we have several participants that will complete all other components of their 6 month follow up visit but will not schedule a time to collect the video with our team. We want to offer \$20 gift cards for completion of 6-month videos to incentivize collection of this data point.
9-1-22	Study	Change in study coordinator from	

Date	Affected Section(s)	Summary of Revisions Made	Rationale
	Coordinator	[name] to [name] (currently KSP).	

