5.0 Enrollment/Randomization

Participants will be enrolled from the Children's Diabetes Program at Vanderbilt.

Due to the COVID-19 pandemic and social distancing requirements, a remote recruitment and enrollment protocol was established. KSP will review the diabetes clinic schedule, and participants who meet initial eligibility criteria (age, date of diagnosis) will be called the week of their clinic visit. The RA will introduce the study, and if mothers are interested, verbal consent for the screening questionnaire will be obtained. Mothers who consent will be emailed a link to the screening survey in REDCap. The RA will then email the mother to let her know if she is eligible or not. Eligible mothers will be asked to schedule a time for enrollment. At the preferred time, the mother and adolescent will be called, and the RA will provide each with a full description of the risks and benefits of the study. If they agree to participate, they will be emailed the link to sign the eConsent form in REDCap. The RA will stay on the phone while these are signed to answer any questions. Once consent/assent forms are signed, the parent and adolescent will be emailed links to complete the study surveys in REDCap. The mother will be asked to text the RA when these are completed or if they have any questions. The final enrollment will take place over the phone (demo text message and Facebook friending).

After completing all baseline data, mothers will be given instructions to "friend" the study Facebook account. Once the mother has established a connection to the study Facebook account, the mother-adolescent dyad will be randomly assigned to the intervention condition or attention control (equal numbers in each group).

Randomization will be stratified by the adolescents' treatment type (insulin pump vs. injections) and use of continuous glucose monitoring (CGM or no CGM) to remove the possibility of confounding by differences related to insulin regimen. Randomization will be determined by a computerized program created by the biostatistician on the project ([name]).

Participating mothers will be mailed a study binder and an A1C mail-in kit within 2-3 days of enrollment.

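### The only stated check of the adolescent self-harm items (YSR 18 and 91) is at enrollment, with no reader or time limit for 3, 6 and 12 months, and the last emergency step has no remote alternative

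*Combined protocol and SAP*

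**What the plan says.** Section 6.0 Study Procedures sets the schedule: "At baseline, 3 months, 6 months, and 12 months, mothers and adolescents will complete surveys". The YSR is listed in that battery as an adolescent measure with no visit restriction. Where a measure belongs to one visit only, as with the Satisfaction Survey, the list says so. The same section places follow-up data collection at routine diabetes clinic visits.

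Section 7.0 Risks opens the adolescent procedure in general terms: "If adolescents endorse items on the Youth Self Report (YSR) measure pertaining to suicide or self-harm, we will follow the following procedure". It then gives the one rule on reading the items: "When the YSR is given during study enrollment, researchers will immediately check items 18 and 91". A score of 1 or 2 on either item leads to paging the clinic social worker and notifying the principal investigator (PI). If the social worker is unavailable, research staff give the Columbia Suicide Severity Rating Scale (C-SSRS). Low risk leads to local resources and a PI check-in within 48 hours. High or ambiguous risk leads back to the social worker, with a final fallback: "If the clinic social worker cannot be reached, the researcher will accompany the patient and their caregiver" to the Children's Emergency Department.

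Section 5.0 Enrollment/Randomization describes a remote enrollment in which "the parent and adolescent will be emailed links to complete the study surveys in REDCap". On completion, "The mother will be asked to text the RA when these are completed or if they have any questions".

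**The concern.** A response procedure works only after someone has seen the answer. Here the duty to respond is general, but the instruction to look is attached to a single contact that precedes randomization. Staff who follow the text literally would check at baseline and would find no instruction for the three later forms. An adolescent who first endorses suicidal thoughts during follow-up would then have no stated time by which a member of staff sees it. The 12-month form is the last one scheduled.

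The second part concerns what happens once risk is recognised. The final step assumes that the researcher and the family are in the same place. Under the remote procedure they are not, even at enrollment, the one contact with a stated check.

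Section 7.0 itself names adolescent depression and reports of self-harm among the possible risks, so the plan recognises the event. What is incomplete is how it is detected and the last step of the response.

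**Working it through.** The documents state no figure to reproduce. The check sets the schedule, the review rule and the response steps side by side.

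**1. Administrations against stated checks** (sections 6.0 and 7.0)

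| YSR administration | Duty to respond if endorsed | Stated reading of items 18 and 91 |
|---|---|---|
| Baseline | Yes | Yes, immediate |
| 3 months | Yes | None |
| 6 months | Yes | None |
| 12 months | Yes | None |

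With a stated check: 1/4 = 25%. Without: 3/4 = 75%.

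The ceiling on forms without a stated check is 3 × 154 planned adolescents = 462. No firm lower figure follows. The sample-size text in section 10.0, written for A1C, expects 130 subjects with 2 to 4 measurements each. If one of those is baseline, that is 1 to 3 follow-up forms each, or 130 × 1 = 130 to 130 × 3 = 390.

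**2. What enrollment means in this protocol.** Section 5.0 treats it as an appointment that is scheduled, is completed by phone with the Facebook connection, and starts the clock for mailing the binder. Randomization follows completion of the baseline data. In that section it is always the baseline contact, not the whole period of participation.

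**3. Which response steps need the adolescent on site**

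- Paging the social worker and notifying the PI: no presence required. The risk assessment follows a clinic protocol that is not reproduced, so whether it works remotely cannot be judged.
- C-SSRS by research staff: possible by phone, though the text does not say so.
- Resources and PI check-in within 48 hours: possible by phone.
- Second contact with the social worker: possible by phone.
- Going with the family to the Emergency Department: presence required.

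So only the last step is clearly unworkable for a remote form. It is reached only if the social worker is unavailable, the C-SSRS shows high or ambiguous risk, and the social worker again cannot be contacted.

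**4. Whether forms are completed remotely.** At enrollment, yes (section 5.0). At follow-up, section 6.0 says clinic visits. The Description of Amendments gives context: the 5-26-20 entry covers remote data collection as well as remote enrollment, and the 3-9-22 entry reports that, after the move to a remote protocol, several participants "will complete all other components of their 6 month follow up visit but will not schedule a time to collect the video". Some remote follow-up is therefore likely, but neither entry says how the follow-up surveys were delivered or reviewed.

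**The case against.** The strongest reply is that the opening sentence of the procedure is unrestricted. Staff cannot honour it without reading the items, so a duty to check at every visit is implied, and enrollment may have been meant loosely as time in the study. The first half of this stands: the obligation to respond covers all four visits. It still supplies no reader and no time, and the loose reading goes against the usage in section 5.0.

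Second, follow-up is placed at clinic visits, where the social worker and the Emergency Department are at hand. This also stands. The problem with the last step belongs to forms completed remotely and is a narrow one.

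Third, a review routine or alert may exist in working procedures outside these documents. That is possible, and the change would then only record it.

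A reader might infer three stronger things that the documents do not support:

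- **That a follow-up answer would wait 3 or 6 months until the next YSR, or stay unseen after the last.** If the later forms have no check, the next form would not reveal the answer either, so those intervals do not follow. The PI also has a general duty in section 7.0 to review data completeness and accuracy, although without stated timing. The delay is unspecified, not known to be long.
- **That a particular number of adolescents would be missed.** No endorsement rate is given, and a probability built on an assumed rate only restates the assumption.
- **That the mothers' PHQ-9 has the same gap.** Section 6.0 says: "Mothers will also complete a measure of depression (PHQ-9) via a link emailed to them by the study team biweekly". But the response in section 7.0 is tied to no visit, has a 48-hour follow-up, and includes referral to an emergency room or crisis hotline. Mothers also have five weekly and two monthly staff calls. The start of the 48 hours could be clearer, but that is a minor matter.

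**Conclusion.** The point holds in a limited form. The protocol commits to responding to any endorsement of items 18 or 91, but it states a check at only 1 of 4 administrations and gives no reader or time limit for the other 3. Separately, the final emergency step has no written alternative for an adolescent who completes the form away from the clinic.

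This rests on four assumptions: the YSR is given at every survey visit, as its unrestricted listing implies; enrollment means the baseline contact; at least some forms are completed remotely, which is certain at enrollment and likely but not documented in section 6.0 at follow-up; and no alert or review routine outside these documents already fills the gap.

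The text does not show that follow-up answers were or would be ignored, or that the whole response chain fails remotely. This is a matter of participant safety, not of analysis: no endpoint, estimate or test changes. It is a cheap improvement that the investigator has good reason to adopt.

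**What to change.** In the self-harm procedure of section 7.0:

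1. Replace the restriction to enrollment with all four visits: baseline, 3, 6 and 12 months.
2. Require review of items 18 and 91 on the day of submission, through an automated REDCap alert to a designated staff role.
3. Add a remote path for forms completed away from the clinic: confirm where the adolescent is, phone the caregiver, give the C-SSRS by phone or video, and direct the family to the nearest emergency service. Using the nearest service matters because the child-protection text in section 7.0 already allows for children living outside Tennessee.

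The cost is a few sentences and one survey alert, with no new data collection. The real burden is staffing: someone must cover alerts at the times when families complete forms from home. If an alert is already in use, the amendment only writes it down.
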